### **(c) Approach**

#### **Preliminary Data in support of this proposal**

Patients with CYP2C19 genotype and PPI exposure in the EHR at UFHealth and Vanderbilt. At UFHealth and Vanderbilt, more than 16,000 patients to date have undergone CYP2C19 testing, with 10,185 being prescribed a PPI. Of these approximately 20% are PMs (1 or 2 LOF alleles), 41% are NMs, and 33% are RMs (1 or 2 GOF alleles), and approximately 7% with genotype combinations with unknown phenotypes. The goal of this analysis will be to evaluate the relationship with overall metabolism (poor vs normal vs rapid) with clinical outcomes. The hypothesis is that PMs will have increased rates of acid suppression and associated increased rates of bone fractures, infection, and chronic kidney disease and dementia while RMs are more likely to develop refractory GERD (inadequate acid suppression) and lower rates of PPI-related complications.

Lansoprazole pharmacokinetic data and CYP2C19 genotype. Table 2 demonstrates the relationship between plasma drug concentrations and CYP2C19 genotype.

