#### Comparison of CYP2C19 SNP Frequencies in Controls vs. Children Undergoing Fundoplication.

**Table 4** shows allele frequencies of CYP2C19 \*2 (LOF) and \*17 (GOF) in children who were on PPIs and who had undergone fundoplication surgery were compared to controls, who were asthmatic patients who participated in the PPI trial . DNA for genotyping was obtained from saliva samples collected from controls, and for cases was obtained from tissue samples collected from children during undoplication surgery. The minor allele frequency of the \*2 (A) allele (PM or IM phenotypes) was underrepresented in the fundoplication cohort compared to controls and the minor allele for the \*17 allele (T) (RM phenotype) was over-represented in the fundoplication cohort compared to controls. These data suggest that RMs are more likely to be undertreated with usual doses of PPI therapy and as a result are subjected to invasive management approaches. In contrast, those with the PM phenotype are effectively treated with a usual dose and so are under-represented in the surgical group. These data could be inferred to suggest that genotype-guided PPI dosing could result in dose increases in RMs, which may have the potential to reduce the number of children who would need to undergo fundoplication surgery.

Collectively, these preliminary data provide compelling evidence for the potential clinical utility of CYP2C19-genotype guided dosing by documenting the relationship between CYP2C19 genotype and PPI pharmacokinetics, that response to PPI therapy, based on gastric pH, is influenced by CYP2C19 genotype, and that patients are undergoing risky, invasive procedures who may simply need a higher dose of PPI to overcome their RM phenotype status.

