Statistical analysis. We will have two primary hypotheses tested in this pragmatic clinical trial: 1. Hypothesis: RMs (1 or 2 GOF alleles) in the genotype-supported arm have better GERD control than RMs in the usual care group 2. Hypothesis: PMs (1 or 2 LOF alleles) in the genotype-supported group have fewer adverse effects (composite of URI/GI infections, kidney adverse effects, bone fracture) than PMs in the usual care group. Continuous variables will be compared between the genotype-supported group and the usual care group using t-test, and categorical variables will be compared using the chi-squared test. The hypotheses will be tested by logistic regression analysis to estimate the odds ratios and 95% confidence intervals for GERD control rate in the RM patients between the two arms and for the adverse events between the PM patients between the two arms. Time to-event analysis will be performed using Kaplan Meier method and a Cox regression model. Significant covariates associated with the events will be adjusted for in the multivariable models. All analysis will be performed in SAS 9.4 (Cary, NC).

We will also have a composite analysis that is conducted in the same manner that combines efficacy and safety and tests the hypothesis that genotype supported PPI dosing leads to better PPI efficacy and safety, as determined by composite of refractory GERD, and adverse effects.

Finally, we will evaluate the influence of genotype-supported dosing recommendations and will evaluate the percentage of the time when a dosing recommendation was made and accepted by the treating clinician, to provide practical data on the willingness of clinicians to adopt this approach. We will also collect patient- and provider-level survey data on attitudes about pharmacogenetics testing; using survey tools adapted from those utilized by other IGNITE groups. These will be shared for network-wide analyses, but because of the number of patients we will study, we should also have sufficient data to perform analyses on our patients along.

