Power calculation. Briefly, with 600 participants in the trial, we will have 80% power at alpha level of 0.05 to detect a relative risk of 1.35 or higher in the GERD control within RM patients in the usual care vs. the genotype-supported arm. This assumes that among the 600 participants, 33% will have the RM phenotype, and half will be randomized to each arm of the study. For the adverse event hypothesis, with 600 patients, we expect to have 178 PM patients, with 89 patients in each arm. At alpha level of 0.05, we will have 80% power to detect relative risk reduction of 29% or more in the adverse events for PM patients in the genotype supported group compared to those in the usual care group.

Clinical Trials.gov. This trial requires registration in ClinicalTrials.gov.

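### The 178 PM patients expected among 600 imply a 29.7% share, but the plan's own frequencies for that group are 20 to 21.7%, which gives 120 to 130

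*Combined protocol and SAP*

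**What the plan says.** All of this is in the Nemours protocol, the second part of the combined document.

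- **Hypothesis.** Under Statistical analysis, the second of two primary hypotheses is that "PMs (1 or 2 LOF alleles) in the genotype-supported group have fewer adverse effects" than the same patients under usual care. Here PM pools intermediate and poor metabolizers.
- **Power.** Under Power calculation, "with 600 patients, we expect to have 178 PM patients, with 89 patients in each arm". The power claim that rests on this count is: "At alpha level of 0.05, we will have 80% power to detect relative risk reduction of 29% or more". The outcome is adverse events, compared between the two arms among PM patients only. No PM frequency, control event rate or sidedness is given.
- **Frequencies.** Under Preliminary Data, for patients with a genotype and a PPI prescription in the health record: "Of these approximately 20% are PMs (1 or 2 LOF alleles), 41% are NMs, and 33% are RMs". Table 1 (Significance section, and also in the UF protocol) lists IM 20%, PM 1.7%, RM 28%, UM 5.3% and `*2/*17` 5.6%.
- **`*2/*17` carriers.** The text below Table 1 leaves them out of the primary analysis because their phenotype is unclear. The Dosing paragraph groups them with normal metabolizers.
- **Trial size.** The Study Design paragraph gives 180 patients (60 children, 120 adults), not 600.

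**The concern.** The power paragraph uses two subgroup shares. The rapid-metabolizer share, 33%, agrees with both of the plan's sources: 33% in the Preliminary Data, and 28% + 5.3% = 33.3% in Table 1. The PM share is not stated, and the count given for it does not agree with those sources.

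Hypothesis 2 is tested only in PM patients, so their number sets its power. The problem is separate from the conflict between 600 and 180. If the total were corrected and the implied 29.7% kept, the plan would expect about 53 PM patients (180 × 0.297), where its own frequencies give 36 to 39.

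**Working it through.** **1. Share implied by the plan's count.** 178/600 = 0.297, or 29.7%; 178/2 = 89 per arm.

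**2. Count from the plan's frequencies, 600 × share.**

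| Source | Share | Count in 600 | Per arm |
|---|---|---|---|
| Preliminary Data, 1 or 2 LOF alleles | 20% | 120 | 60 |
| Table 1, IM + PM | 20% + 1.7% = 21.7% | 130 | 65 |
| Table 1, IM + PM, rescaled after removing `*2/*17` | 21.7/94.4 = 23.0% | 138 | 69 |
| Table 1, IM + PM + all `*2/*17` | 27.3% | 164 | 82 |

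None gives 178. Against 120 to 130, it is too high by 178/130 − 1 = 37% to 178/120 − 1 = 48%. Reaching 178 would take 178/0.217 = 820 to 178/0.20 = 890 participants.

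**3. The plan's power statement.** With no event rate stated, I solved for the control rate p1 that makes the claim true. The inputs are n = 89 per arm, p2 = 0.71 × p1, two-sided alpha 0.05 and power 80%. With p̄ = (p1 + p2)/2, the two-proportion formula is

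power = Φ{[(p1 − p2) − 1.96 √(2 p̄(1 − p̄)/n)] / √([p1(1 − p1) + p2(1 − p2)]/n)}.

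This gives p1 = 0.704 and p2 = 0.500. Check at n = 89: (0.204 − 1.96 × 0.0734)/0.0718 = 0.84, and Φ(0.84) = 0.80.

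**4. Same assumed rates, corrected numbers.**

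| Total | PM patients | n per arm | Power for a 29% reduction | Reduction detectable at 80% power |
|---|---|---|---|---|
| 600, as stated | 178 | 89 | 80% | 29% |
| 600, share 21.7% | 130 | 65 | 67% | 34.1% |
| 600, share 20% | 120 | 60 | 63% | 35.5% |
| 180, share 21.7% | 39 | 19.5 | 25% | 62% |
| 180, share 20% | 36 | 18 | 23% | 64% |

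**5. Sensitivity to the unstated choices.** A one-sided test back-solves to a control rate of 0.636. At 600 it then gives 65 to 68% power and a detectable reduction of 33.9 to 35.3%. A continuity correction moves the back-solved rate to about 0.74. The control rate is therefore uncertain, but fewer PM patients mean less power at any rate.

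**The case against.** **The plan contains higher LOF figures.** The Statistical analysis paragraph does not itself exclude `*2/*17`, and a literal reading of one or two LOF alleles gives 27.3%, or 164. The control children in the fundoplication comparison (UF protocol, Preliminary Data) show (75 + 4)/278 = 28.4% `*2` carriers, or 171. Under the assumed rates those counts would keep power at about 77 to 78%. This narrows the gap, but neither figure reaches 178, and both include `*2/*17`, which the Significance section excludes. Removing the `*2/*17` share expected from that table's allele frequencies under random pairing, 2 × 0.149 × 0.200 = 6.0%, leaves about 22.5%, or 135. The only share above 29.7% is 13 of 41 (31.7%, or 190) in the small pharmacokinetic sample of Table 2, and it does not reproduce 178 either.

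**The source population may not fit.** Table 1 comes from UF clopidogrel testing, while the 600-patient plan included 250 children (enrolment estimate in the Nemours protocol). That is a fair limitation. However, the plan offers no other source for the PM count, and the RM share in the same paragraph agrees with Table 1.

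**The 600 is out of line anyway.** This stands. At 180, keeping 29.7% gives about 27 per arm and 33% power, against 23 to 25% after correction. Hypothesis 2 is badly underpowered either way, mainly because of the total. The share still has to be corrected, because rescaling the total alone would carry the error forward.

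**A stronger reading.** A reader might infer that recruiting patients who have failed a PPI pushes the share lower still, since the plan says "those with the PM phenotype are effectively treated with a usual dose and so are under-represented in the surgical group". The documents do not support using this. Eligibility also covers patients starting a PPI, the paediatric criterion does not require PPI failure, and the mix is not given. The 8.8% LOF share among fundoplication patients is 3 of 34 surgical children and is no proxy for clinic enrolment.

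**Conclusion.** The count of 178 is wrong against the plan's own frequencies. For the group as defined, with `*2/*17` excluded, 600 patients would yield 120 to 130 PM patients. No frequency in the documents reproduces 178. This conclusion needs no assumption beyond the plan's figures.

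The effect on power is an illustration. If the control rate is about 0.70 and the test two-sided at 0.05, the stated 80% becomes about 63 to 67% at 600, with a detectable reduction of about 34 to 36%. At 180 it becomes about 23 to 25%, with a detectable reduction of about 62 to 64%. A reader might take 0.70 as the plan's event rate, but it is only the value that makes the plan's claim consistent. The 600-patient figures also describe a trial larger than the one now set out.

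**What to change.** In the Nemours Power calculation paragraph:

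1. Replace the PM count with one based on 20 to 21.7%, `*2/*17` excluded, applied to the actual planned total, and name the source of the frequency. At 180 this is 36 to 39 patients, 18 to 20 per arm.
2. State in Statistical analysis that `*2/*17` carriers are outside the hypothesis 2 group, so that the definition matches the Significance section.
3. State the assumed control event rate with its source, and whether the test is one- or two-sided.
4. Restate the PM number per arm and the detectable reduction, or the power, for hypothesis 2.

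This is a text correction with a short recalculation. It changes no procedure or data collection. Its cost is that the stated figures become less favourable.

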Assessment of PPI efficacy and adverse effects. Our primary outcome will be the effectiveness of PPI therapy, which will be determined via two questionnaires: RDQ and GOS scale, administered by study personnel at baseline and 12 weeks. The RDQ was developed to monitor treatment response over time and evaluates 6 symptoms (12 items) covering 3 domains: heartburn, regurgitation, and upper abdominal pain. Each symptom is evaluated using a 6-point Likert scale to assess frequency and severity over the previous week. Each symptom is rated from 1 (did not have) to 6 (severe), and the RDQ mean score is calculated as the mean response to the 12 items. The RDQ mean score thus ranges from 1 to 6 and has been psychometrically validated. The GOS scale evaluates 18 symptoms, with each rated from 1 (no problem) to 7 (very severe). Similar to the RDQ, the mean score is calculated as the mean response to the 18 items, with mean scores ranging from 1 to 7. Patient participation will end after they complete the approximate 12 week questionnaire. However, we will continue to

follow patients over 24 months through medical record review to assess adverse outcomes for occurrence of upper respiratory infection (cold), sore throat, strep throat, bronchitis, pneumonia, ear infection, acute sinusitis (sinus infection), bone fractures, renal function and gastrointestinal infections.

Metrics for assessing success of pharmacogenetic testing in clinical practice. We will test a variety of variables that will provide insight into attitudes and acceptability of pharmacogenetic testing. These will include: 1) percent of patients approached about the study who agree to participate; 2) surveys of patients and clinic staff on knowledge, attitudes, and beliefs about pharmacogenetic testing; and 3) the percent of the time a dosing recommendation for a patient in the genotype-supported arm is accepted by the clinician. Patients will be surveyed about knowledge, attitudes, and beliefs about pharmacogenetic testing using questionnaires on enrollment and at the end of their study participation. Clinic staff will be surveyed about knowledge, attitudes, and beliefs about testing at the beginning and end of the study.

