With 180 total patients (90 patients in each arm), we expect approximately 30 patients in each arm to have the genotype of interest (i.e. RM or UM). At alpha of 0.05, we will have 80% power to detect effect size of  $\geq 0.74$  in the RDQ score in RMs/UMs. This effect size is equivalent to a RDQ score difference of 1.22 for regurgitation and a score difference of 0.93 for heart burn. These differences in RDQ scores are smaller than what is considered clinically significant. Therefore our study is well-powered.

In summary, by studying a total 180 patients (120 from UF Health and 60 from Nemours), the data suggest we will have excellent power to detect an efficacy endpoint. Data generated from this protocol on adverse effects will also help us define the incidence of the adverse effect phenotypes to inform sample size for a future pragmatic trial examining effects of genotype-supported dosing on PPI safety endpoints.

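### The Nemours claim of 80% power for a 29% cut in adverse events among PMs rests on an unstated usual-care risk of about 70% and on 89 PMs per arm, which a 180-patient trial will not supply

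*Combined protocol and SAP*

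**What the plan says.** In the Nemours protocol, Statistical analysis names two primary hypotheses. The second is that PMs in the genotype-supported arm have fewer adverse effects than PMs under usual care, the outcome being a "composite of URI/GI infections, kidney adverse effects, bone fracture". Logistic regression is the test for the hypotheses, "categorical variables will be compared using the chi-squared test", and Kaplan-Meier and Cox analyses are also listed.

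Power calculation then says: "with 600 patients, we expect to have 178 PM patients, with 89 patients in each arm", and, at an alpha of 0.05, "we will have 80% power to detect relative risk reduction of 29% or more in the adverse events for PM patients". It gives no usual-care event risk, no time window and no statement of whether the test is one- or two-sided.

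Other parts of the file bear on these inputs:

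- Nemours protocol, Study Design: 180 patients (60 children, 120 adults), with health-record data on adverse outcomes for up to 24 months.
- Nemours protocol, Assessment of PPI adverse events and efficacy: weekly questionnaires on infections for up to 12 weeks.
- Nemours protocol, preliminary data: about 20% of genotyped, PPI-treated patients are PMs. Table 1 gives 20% IM plus 1.7% PM, which is 21.7% under the protocol's grouping of all loss-of-function carriers as PMs.
- Adult protocol, Research Plan: investigators will "follow patients over 24 months through medical record review to assess adverse outcomes". Its power section says the trial's data will "help us define the incidence of the adverse effect phenotypes" for a future trial.

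**The concern.** A relative reduction cannot be turned into power without the control-arm risk. A reader given only 29%, 80% and 89 per arm cannot tell how many events the claim needs, or whether 12 weeks or 24 months of follow-up is meant to produce them. The 600 participants behind the 89 per arm are also more than three times the number the same protocol plans to randomize.

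This matters because the hypothesis is one of two called primary. If the trial found no significant difference in adverse events, a reader relying on the stated 80% could take that as fair evidence against a safety benefit, when the test may have had little chance of detecting one.

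**Working it through.** **Inputs.** From Power calculation: n = 89 per arm, alpha 0.05, power 80%, relative risk 0.71. Two-sided testing is assumed because the text does not say. The usual-care risk p₁ is not given, so it has to be solved for.

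**Formula.** Two-proportion test with pooled null variance, p₂ = 0.71 p₁, p̄ = (p₁ + p₂)/2:

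Power = Φ{ [p₁ − p₂ − 1.960 √(2p̄(1 − p̄)/n)] / √([p₁(1 − p₁) + p₂(1 − p₂)]/n) }

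**Step 1: reproduce the 80%.** Solving for p₁ gives 0.704 against 0.500. The difference is 0.2042 and the two standard errors are 0.0734 and 0.0718. Then (0.2042 − 1.960 × 0.0734)/0.0718 = 0.84, and Φ(0.84) = 0.80. This implies 89 × 0.704 × 1.71 ≈ 107 events among 178 PMs.

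Other two-sided methods (unpooled, arcsine, log odds ratio, log relative risk, continuity-corrected) put the required risk between 69.6% and 73.4%. One-sided, it is 63.6%. A log-rank reading with hazard ratio 0.71 needs 4(1.960 + 0.842)²/(ln 0.71)² ≈ 268 events, more than the 178 PMs, so the Cox analysis does not explain the figure.

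**Step 2: other risks at 89 per arm.** At p₁ = 0.30, p₂ = 0.213: (0.087 − 1.960 × 0.0655)/0.0651 = −0.63, so power is 26%. All risks in this table are assumptions.

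| Usual-care risk | Power for a 29% reduction | Expected events (89 × p₁ × 1.71) |
|---|---|---|
| 70% | 79% | 107 |
| 60% | 64% | 91 |
| 50% | 50% | 76 |
| 40% | 37% | 61 |
| 30% | 26% | 46 |
| 20% | 17.5% | 30 |

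The reduction detectable with 80% power at 89 per arm is 41% at a 50% risk, 57% at 30% and 70% at 20%.

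**Step 3: the PM count.** 178/600 = 29.7%, above both 20% and 21.7%. With 180 patients, 180 × 0.20/2 = 18.0 and 180 × 0.217/2 = 19.5 per arm.

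**Step 4: power at that count.** At p₁ = 0.70 and n = 18, both standard errors grow by √(89/18) = 2.22, to 0.163 and 0.160. Then (0.203 − 1.960 × 0.163)/0.160 ≈ −0.73, so power is 23%.

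| Usual-care risk | 18.0 per arm | 19.5 per arm |
|---|---|---|
| 70% | 23% | 25% |
| 50% | 14% | 15% |
| 30% | 9% | 9% |

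Even as the risk approaches 100%, two-sided power reaches only about 71% to 76% with 18 to 20 per arm. Keeping the plan's own 29.7% share (26.7 per arm) gives 32% at a 70% risk and 11% at 30%.

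The same formula, solved for p₂ at 80% power, gives detectable reductions of about 62% to 64% at a 70% risk and 80% to 82% at 50%. At a 30% risk no reduction is enough. With p₂ = 0 and n = 18, (0.300 − 1.960 × 0.119)/0.108 = 0.62, a power of 73%. The normal approximation is rough at this size, so these are orders of magnitude.

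**The case against.** The strongest reply is that 70% is undisclosed, not shown to be false. The composite counts any upper respiratory or gastrointestinal infection. The questionnaire asks weekly about colds, sore throat, ear infection, sinusitis and gastroenteritis, and records may be followed for 24 months. The investigators say they used this questionnaire in a cited paediatric PPI trial, which could supply a rate. The power paragraph presents itself as a summary, and a page of the Nemours design section was not available. This stands: a reader might infer that 70% is impossible or that the 80% is an arithmetic slip, and the documents support neither.

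The adult protocol's remark about defining incidence also needs care. It concerns a future trial, and it does not show that the Nemours authors had no working rate. It shows only that the companion protocol treats the incidence as something to be learned.

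A reader might also infer that the missing risk is a problem independent of sample size. It is not. The 70% is solved from 89 per arm and moves with that number. With the PM share corrected but 600 patients kept (about 60 to 65 per arm), it becomes about 79% to 81%. With 180 patients, no risk gives 80% power two-sided. Nor can the 70% be divided between adults and children to test it: the two protocols collect events differently, and neither gives PM shares by site.

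None of this restores the claim. A high rate may be possible, but it is not stated, and the trial does not have the PMs.

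**Conclusion.** The 80% power claim for a 29% reduction is not supported. At 89 per arm it depends on an undisclosed usual-care risk of about 70% (about 64% if one-sided). At the roughly 18 to 20 PMs per arm expected from 180 patients, power is about 23% to 25% at that same risk and about 9% at 30%, and 80% is out of reach at any realistic risk.

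These figures assume a two-sided 0.05 test, 1:1 allocation among PMs, PM shares of 20% to 21.7% and no dropout. One-sided testing raises power at 89 per arm and a 30% risk to about 38%, which does not change the conclusion. Every risk other than the back-solved 70% is an assumption, because the available text gives no composite event rate.

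**What to change.** In the Nemours Power calculation:

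1. Withdraw the statement of 80% power for a 29% reduction.
2. State the assumed usual-care risk among PMs, its source, its time window (12 weeks or 24 months) and whether the test is two-sided.
3. Give power, or the detectable reduction, over a range of risks such as 20% to 70%, at the PM count expected from 180 patients.
4. If no risk can be supported before the trial, present the second primary hypothesis as estimation with a confidence interval and make no power claim for it.

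The cost is a rewritten paragraph and a less favourable stated figure. No extra patients or data collection are needed.
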